Bacterial load (organism quantities are listed as scant, moderate, or heavy), identification of organism, and susceptibility will be analyzed and reported by the University of Missouri Hospital Laboratory, via semiquantitative wound culture(s) done at each debridement procedure. A maximum of 3 wound cultures will be used for the purposes of research, and the sponsor will cover the cost of up to 3 wound cultures. The culture will be done in the OR, after negative pressure dressing removal, prior to surgical prepping.

The subject will sign consent, be enrolled, and then be randomized at the pre-operative/screening visit. During the initial surgical debridement procedure, information about the wound characteristics, the wound culture results, and information about the dressing that is placed in the OR will be collected for research purposes.

Wound healing will be evaluated at weekly intervals until the sutures are removed and the wound is deemed healed. To assess wound healing, weekly photos of the wound/incision will be done either in clinic, or will be obtained from the subject after they take the photo at home. When applicable, weekly phone visits will be completed to obtain a photo of the incision, (starting after discharge from the hospital), until the subject returns for their SOC clinic visit for suture removal (around 3 weeks post-op). The wound/incision will be assessed with a VAS Incision Healing Assessment Form.

Clinical follow-up visits will be standard after wound healing with clinical radiographs to document fracture healing--6 weeks after initial surgery (+/- 1 week), 3 months (+/-1 week), 6 months (+/-2 weeks), and 12 months (+/-2 weeks) or until fracture healing with minimum of 6 months f/u. Any further debridement or procedures done for fracture healing, including bone stimulator use, will be documented. A clinical photo(s) will be taken at all visits following the initial surgical debridement to document wound healing.

Primary Endpoints:

1. Time to wound and fracture healing (indicating successful resolution of infection)
2. Bacterial load (organism quantities are listed as scant, moderate, or heavy)

Secondary Endpoints:

Number of surgeries:

1. # of operative debridements until wound healed
2. # of surgeries for fracture healing (nonunion and bone grafting)
3. VAS (Incision Healing Assessment Form) scores, based on standardized digital image

Inclusion/Exclusion Criteria

Inclusion:

- Patients 18 years and older

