- Patients who will be undergoing surgical management (including the use of NPWT therapy) of an infected lower extremity status-post open reduction and internal fixation (ORIF)

Exclusion:

- Pregnant females
- Incarcerated patients and those not able to give informed consent

Withdrawal of Subjects: Subjects will be informed that they have the right to withdraw from the study at any time for any reason, without prejudice to their medical care. The Investigator(s) may elect at any time to withdraw a subject from the study for any reason unrelated to the study if such a decision is in the subject's best medical interest. If a subject discontinues the study prematurely, or is withdrawn by the Investigator(s), as much follow-up data as possible will be obtained. The primary reason for termination or discontinuation will be documented in the report of the final results.

Safety:

Adverse Events:

If an AE/SAE occurs, the details will be collected on an AE/SAE form.

An adverse effect (AE) is any undesirable experience (e.g., sign, symptom, illness, clinically significant abnormal laboratory value, or other medical event) occurring in a subject during the course of the study, whether or not it is related to the investigational device or procedure.

An AE does include a/an:

- Exacerbation of a pre-existing illness
- Increase in frequency or intensity of a pre-existing episodic event or condition
- Condition detected or diagnosed after study device use even though it may have been present prior to the start of the study
- Continuous persistent disease or symptoms present at baseline that worsen following the start of the study

An AE does not include a/an:

- Medical or surgical procedure (e.g., surgery, endoscopy, transfusion); the condition that leads to the procedure is considered an AE

- Pre-existing diseases or conditions present or detected at the start of the study that do not worsen
- Situations where an untoward medical occurrence has not occurred (e.g., hospitalizations for cosmetic elective surgery, social and/or convenience admissions)
- The disease or disorder being studied, or sign or symptom associated with the disease or disorder, unless the disease, sign or symptom is more severe than expected based on the subject's condition and/or requires intervention.

Serious Adverse Events:

A Serious adverse event is an adverse event that:

- Led to death,
- Led to serious deterioration in the health of a subject that

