 - resulted in a life-threatening illness or injury,
 - resulted in permanent impairment of a body structure or body function,
 - required inpatient hospitalization or prolongation of existing hospitalization, or
 - resulted in medical or surgical intervention to prevent permanent impairment to a body structure or a body function.
 - Led to fetal distress, fetal death or a congenital anomaly or birth defect.

The following clarifications are provided for the serious adverse events:

- Life-threatening means that the subject was, in the view of the Investigator, at immediate risk of death from the event as it occurred. The definition does not include an event that, had it occurred in a more severe form, might have caused death.
- Hospitalization for elective treatment of a pre-existing condition that did not worsen during the study is not considered a serious adverse event.
- "Inpatient" hospitalization means the subject has been formally admitted to a hospital for medical reasons. This may or may not be overnight. It does not include presentation at a casualty or emergency room.
- Important medical events that may not result in death, or be life-threatening, however based upon appropriate medical judgment, may jeopardize the subject and may require medical or surgical intervention to prevent one of the outcomes listed in this definition.
- Is significant for any other reason.

Anticipated Adverse Events:

Anticipated adverse events are those events that are reasonably expected to occur as a result of the subject's disease state or treatment. For this study, anticipated

adverse events associated with the procedure or post-procedure include, but are not limited to, the following;

- Infections, both deep and superficial
- Allergies or other reaction to device materials
- Temporary or permanent nerve damage as a result of pressure or hematoma.
- Cardiovascular complications including venous thrombosis, pulmonary embolism, and cardiac arrest.
- Wound hematoma and delayed wound healing.

Device-related adverse events are those events that can be directly attributed to the study device and are adjudicated as such by the Investigator. These events may include, but are not limited to:

- Infections, both deep and superficial
- Allergies or other reaction to device materials
- Loosening of the implant as a result of changed condition in load transfer, respectively fatigue wear or tissue reaction to implant or as result of inadequate anchoring technique.

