Skin and Subcutaneous Tissue Reaction/Allergy	
• Desiccation/injury• Skin rash, irritation, blistering• Pruritus/itching• Skin excoriation/breakdown• Skin stripping• Skin scarring if significant skin irritation were to occur• Maceration• Skin hyper/hypo-pigmentation at and/or around dressing application area• Erythema/redness, edema, inflammation, or swelling at and/or around dressing application area
Mild Pain or Discomfort	
• Tenderness/minor ache at and/or around dressing application area• Perspiration associated with wearing dressing• Auditory irritation (due to mild buzzing sound of negative pressure unit)• Decreased sleep or sleep quality• Paresthesia (numbness, tingling, prickling, creeping sensation)

Other	
 • Bleeding • Cardiac compromise (vagal response, bradycardia) • Pulmonary compromise • Accidental instillation in a body cavity • Localized infection • Autonomic dysreflexia (in subjects with spinal cord injury) • Retained foreign debris (e.g.foam) in the wound • Impairment of mobility/activity (limitation secondary to weight and attachment of therapy unit) • Possible tubing entanglement/trip or slip hazard leading to fracture, tissue damage • Incorrect therapy unit settings resulting in incorrect frequency/dosing • Tunneling • Stalled healing/non-progression of healing • Deterioration of the wound • Systemic reaction (due to allergic reaction to dressing materials) • Burn secondary to therapy unit or power cord malfunction
-------	---

Prontosan:

In very rare cases there may be a mild burning sensation after Prontosan is applied. This should subside after a few minutes. In Rare cases (less than 1 out of 10,000), anaphylactic shock has been reported after the use of Prontosan. Protosan can also cause allergic reactions such as itching and rashes.

Quality Assurance of Data Collection:

Patient confidentiality is maintained by adherence to the rules of HIPAA and the University of Missouri IRB. Close assessment of perioperative events and complications will be performed to ensure no significant deleterious effects are resulting from research activity.

Statistical analysis plan:

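### The exclusion list does not address known hypersensitivity to Prontosan, although the protocol names anaphylactic shock as a risk and only the VeraFlo arm receives the product

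*Protocol*

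**What the plan says.** Eligibility is set out in full under Inclusion/Exclusion Criteria in the protocol. There are two inclusion criteria: "Patients 18 years and older" and "Patients who will be undergoing surgical management (including the use of NPWT therapy) of an infected lower extremity" after open reduction and internal fixation. There are two exclusion bullets: "Pregnant females" and "Incarcerated patients and those not able to give informed consent".

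Under Study Design, patients are randomised to VeraFlo with Prontosan or to standard negative pressure, 10 per group. Up to 30 may be enrolled to reach 20 completed subjects. Randomisation follows consent, at the pre-operative/screening visit.

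The Prontosan paragraph of the risk text says: "In Rare cases (less than 1 out of 10,000), anaphylactic shock has been reported after the use of Prontosan". It also names itching and rashes as allergic reactions, without a rate. The table of NPWT risks includes "Systemic reaction (due to allergic reaction to dressing materials)". The lists of anticipated and of device-related adverse events both contain "Allergies or other reaction to device materials".

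**The concern.** The protocol recognises a serious allergic risk with the product under test but does not carry it into eligibility. A patient whose record shows a reaction to Prontosan satisfies every criterion as written.

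Two things are at stake. One is safety, since such a patient could be exposed to a product to which they are known to react. The other is the comparison. Prontosan is the element that randomisation assigns, so a known reactor could receive one allocation but not the other. Any resulting non-adherence or withdrawal would fall on VeraFlo alone.

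**Working it through.** The plan gives no figure on this point to reproduce. The check is mainly a reading of the text, with one bound.

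**1. Does any criterion cover it?** No. Age, planned surgery with NPWT, pregnancy, incarceration and inability to consent are the only conditions, and none mentions allergy or contraindication.

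**2. Does any other text close the gap?**
- *Enrolment procedure (Study Design):* consent, enrolment and randomisation are described without an allergy check. The patient characteristics named for collection are weight, BMI, comorbidities and smoking status.
- *Withdrawal of Subjects:* the investigator may withdraw a subject in the subject's best medical interest. This acts after enrolment and is worded for reasons not related to the study, so it is not an eligibility rule and does not clearly reach intolerance of the study product.
- *Dressing rule (Study Design):* enrolled participants may have only the dressing of their randomised arm. No alternative is described for a VeraFlo patient who cannot have Prontosan.
- *A separate SAP:* if one exists, it would not set eligibility.

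**3. What happens to a known reactor once randomised?**

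| | Allocated to VeraFlo | Allocated to standard NPWT |
|---|---|---|
| Allergy not noticed | exposed to Prontosan | no Prontosan, treated as assigned |
| Allergy noticed after allocation | cannot receive assigned treatment | treated as assigned |

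The two outcomes in the VeraFlo column are alternatives for any one patient. Both occur in that column only, and a check before randomisation removes both.

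**4. How many such patients?** The documents give no frequency of known reactors. The only rate is below 1 in 10,000, for anaphylactic shock. As a generous assumption, suppose that every enrolled patient had used Prontosan before and that the rate applies per user:
- 20 patients: expected number with prior anaphylaxis below 20 × 1/10,000 = 0.002
- 30 patients: below 30 × 1/10,000 = 0.003

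With equal allocation, half of these would be assigned to VeraFlo: below 0.001 to 0.0015. The bound does not cover itching and rash, for which no rate is given. It is an expected count of patients with that history. It does not describe the risk on re-exposure, because the rate is stated without reference to allergy history.

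**The case against.** The strongest reply is that the event is very rare on the only documented rate, that this is a declared pilot, and that a careful surgeon would consult the allergy record anyway. The protocol also refers to product information and instructions for use, which are not at hand. Enrolling up to 30 to reach 20 completers leaves room for an occasional loss. No endpoint, test or stated figure is affected.

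Most of this stands, and it limits the size of the point. It does not remove it. Informal practice is not part of the criteria, and replacing a lost VeraFlo patient restores the count but does not undo a selective loss.

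A reader might infer more than the documents support:
- *That the eligibility and risk sections contradict each other.* They do not. A list of possible reactions does not by itself require matching exclusions. Bleeding and cardiac compromise are also listed as risks without any.
- *That dressing materials raise the same problem.* This is much weaker. NPWT is planned for every eligible patient and given in both arms, so allergy to those materials would probably be considered before enrolment. For materials common to both arms, the argument about one-sided loss does not apply. The documents do not say how far the two dressings differ.
- *That sites would necessarily randomise a known reactor.* The criteria permit this but do not compel it.
- *That the amount of exposure or the small arms measure the effect.* A 2 hour cycle over 72 to 96 hours gives 72/2 = 36 to 96/2 = 48 instillations, and one patient is 1/10 = 10% of the arm. But no risk per instillation is given, and the 10% presupposes that such a patient is enrolled. Neither shows a likely effect.

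**Conclusion.** The point holds for Prontosan. As written, the criteria admit a patient with known hypersensitivity to it, the protocol's own risk text names anaphylactic shock and allergic reactions, and nothing else in the document closes the gap. For any such patient allocated to VeraFlo, the result is either avoidable exposure or a one-sided inability to receive the allocation.

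The expected number in 20 to 30 patients is probably very small. This rests on the stated anaphylaxis rate and on a judgement that known milder reactions are also uncommon, which the documents neither confirm nor refute. The change is still worth making because the possible consequence is serious and the remedy costs almost nothing. It is a safety and eligibility point with a minor bearing on the comparison.

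**What to change.** Reconcile the eligibility criteria with the protocol's risk text by adding a criterion on known hypersensitivity to Prontosan. Check it from the allergy record for all patients before randomisation, so that both arms contain only patients able to receive either allocation. The sponsor and investigator should set the exact clinical wording, and should decide whether it also covers the dressing materials common to both arms.

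The cost is one line in the protocol, one screening check per patient and a negligible loss of recruitment. No sample size or analysis changes.

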dressings. Unlike other antiseptics, the antimicrobial efficacy of Prontosan® is not impaired in human wound fluid, human tissue or by high loads of blood or albumin. Furthermore, Prontosan® blocks the microbial attachment to surfaces and has been shown to effectively remove biofilms in vitro and in vivo (Hubner *et al* 2010).

Study Recruitment: 20 subjects, not including screen failures. The small sample size will serve as a pilot study to determine an adequately powered study after completion.

Study Design: The objective of this study is to determine if Prontosan instillations (in conjunction with NPWT treatment) decrease time to wound and fracture healing and decrease bacterial load compared to NPWT treatment without Prontosan.

With IRB approval, up to 30 patients will consent and enroll, with a goal of 20 completed subjects. Patients with infected lower extremity wounds, status-post ORIF, undergoing standard of care operative debridement will be enrolled and randomized to either the VeraFlo with Prontosan group or standard negative pressure group. There will be 10 patients in each group. The standard negative pressure group will receive the V.A.C Ultra Negative Pressure Wound Therapy System. NPWT device settings for both arms will be 125mmHg. The following setting will be used for the VeraFlo group: Prontosan, 20min dwell time 2 hour cycle. The amount of Prontosan to be infused is based on the size of the wound and will vary between subjects.

Subject weight, BMI, comorbidities, and smoking status will be collected from the medical record and/or the subject, and will be used for research purposes.

All NPWT dressings will be applied sterilely in the OR after debridement and irrigation per standard of care practice. Only the standard negative pressure device or Veraflo dressing may be used on enrolled participants (based on randomization designation), without any silver dressing, Adaptec or Xeroflo. Dressings will be changed every 72 to 96 hours (based on patient progress and clinical presentation) in the OR for a minimum of 1 more debridement (indicating at least one debridement and NPWT application).

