- Dislocation, subluxation or inadequate scope of movement as a result of failure to achieve optimum positioning of the implant.
- Bone fractures as a result of one-sided overload or weakened bone structure.
- Temporary or permanent nerve damage as a result of pressure or hematoma.
- Wound hematoma and delayed wound healing.

Unanticipated Adverse Events:

An Unexpected Adverse Experience (UAE) is defined as any adverse reaction, the nature and severity of which is not consistent with the applicable product information. These events will be documented as described below.

An Unexpected Adverse Device Effect (UADE) is defined as any adverse effect on the study subject's health or safety, or any life-threatening problem or death caused by or associated with the device. Also, the effect must not have been previously identified in the Investigational Plan or Instructions for Use in its nature, frequency or severity. UADEs may also include other serious problems associated with the device that affect the rights or welfare of study subjects.

Adverse Event Documentation:

The Principal Investigator or designee will report adverse events for the study analysis. Adverse events will be evaluated and differentiated by:

- Severity of the event, defined below.

- Mild: Awareness of signs and symptoms, but easily tolerated; are of minor irritant type, causing no loss of time from normal activities; symptoms would not require medication or a medical evaluation; signs and symptoms are transient.
- Moderate: Discomfort severe enough to cause interference with usual activities; requiring treatment, but not extended hospitalization or intensive care for the subject.
- Severe: Incapacitating with inability to do work or usual activities; signs and symptoms may be systemic in nature or require medical evaluation and/or treatment; requiring additional hospitalization or intensive care (prolonged hospitalization).
 - Serious Code, as defined in Section “Serious Adverse Events”
 - Relatedness to the device or procedure, defined as:
 - Unrelated: AE is due to the underlying disease state or concomitant medication or therapy not related to the study-specific devices or procedures.
 - Probably not Related: AE had minimum or no temporal relationship to the study-specific devices or procedures and/or more likely alternative etiology exists.

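### Three of the seven example device-related adverse events describe an implant, not the NPWT/VeraFlo systems under study, which could make such events count as expected device effects

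*Protocol*

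**What the plan says.** **Study devices.** Protocol, Study Design: "The standard negative pressure group will receive the V.A.C Ultra Negative Pressure Wound Therapy System". The other arm receives VeraFlo with Prontosan. The same section adds: "Only the standard negative pressure device or Veraflo dressing may be used on enrolled participants". Under the inclusion criteria, patients have already had internal fixation when they enter, so the hardware is neither assigned nor compared.

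**The list.** Protocol, Safety, Anticipated Adverse Events: "Device-related adverse events are those events that can be directly attributed to the study device and are adjudicated as such by the Investigator". An open-ended list of seven examples follows. Three of them are:

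- on loosening, "Loosening of the implant as a result of changed condition in load transfer, respectively fatigue wear or tissue reaction to implant" (the item also refers to how the implant was anchored);
- on implant position, "Dislocation, subluxation or inadequate scope of movement as a result of failure to achieve optimum positioning of the implant";
- on fracture, an item that names uneven loading or weak bone as the cause.

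The other four are infection, allergy or reaction to device materials, nerve damage, and wound hematoma with delayed healing.

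**The NPWT risks.** A separate table, Risks Associated With NPWT Therapy/Dressing, gives the hazards of the actual devices, for example "Accidental instillation in a body cavity", bleeding, retained foam and incorrect unit settings. A Prontosan paragraph follows it and covers allergic reactions and anaphylactic shock.

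**The rules that use prior identification.** Both UADE definitions exclude an effect already identified in the investigational plan. The Expectedness section calls a serious event expected if the study or product documentation has already identified it. The 24-hour report to the sponsor covers severe adverse events and unanticipated device-related events.

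**The concern.** A foam dressing with a suction or instillation unit has no anchoring, no load transfer and no implant position. The three items therefore cannot describe the study device by the mechanisms they state. They read like text carried over from an implant study. The Safety section also assigns regulatory reports to a company that appears nowhere else in the protocol, which fits that explanation but does not prove it.

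The error would be cosmetic if the list had no function. But both the UADE definitions and the expectedness rule ask whether the plan has already identified the event, and this list is part of the plan. The population makes the question a live one: patients have infected fractures with hardware in place, fracture healing is part of a primary endpoint, and follow-up runs for at least 6 months. Loosening or re-fracture is a plausible event, and the trial would want to know if the therapy contributed to it. What is at stake is how such an event is labelled and, in some cases, how fast the sponsor hears of it.

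**Working it through.** There is no figure in the plan to reproduce. The check is a count, followed by a reading of the rules in sequence.

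**Step 1: count the device-related list.** The items are (1) infections, (2) allergies or reactions, (3) implant loosening, (4) dislocation or subluxation, (5) bone fracture, (6) nerve damage, (7) hematoma and delayed healing. Items 3, 4 and 5 are implant or loading mechanisms: 3 / 7 = 43%. The remaining 4 / 7 = 57% can apply to NPWT.

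**Step 2: compare with the NPWT risk table.** Its Other row has 15 entries. Clear counterparts in the device-related list are localized infection, stalled healing and systemic allergic reaction; bleeding overlaps in part with wound hematoma. Retained foam, accidental instillation and incorrect settings have none. The table does mention fracture, but after a tubing trip or slip, which is a different mechanism from overload or weakened bone.

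**Step 3: follow one event through the rules.** Take a hardware loosening or re-fracture and compare its handling with the three items in the list and without them.

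| Step | Items in the list | Items deleted |
|---|---|---|
| Relatedness | Judged by the investigator | Judged by the investigator |
| If serious: report to KCI and the IRB | Yes | Yes |
| If graded severe: 24-hour report to sponsor | Yes | Yes |
| If judged device-related: identified in the plan as a device effect? | Arguably yes | No, for the overload mechanism |
| UADE or unexpected | Could be denied | Open to be met |
| If device-related and mild or moderate: 24-hour report | Could be missed | Required, as unanticipated |

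The first three rows do not change; the last three can. The affected set is therefore events judged device-related, and for the 24-hour report only those graded below severe. The severity scale places events that need additional hospitalization under severe, so most admissions for hardware failure would still be reported within 24 hours.

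**The case against.** Several stronger readings are tempting, and the protocol does not support them.

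- *The list makes hardware failure attributable to the device.* It does not. The list is illustrative, the investigator must adjudicate, and every event is graded on a five-category relatedness scale that includes unrelated.
- *The safety signal is lost.* It is not. Serious events go to KCI and the IRB whatever their expectedness. Radiographs are scheduled, further procedures for fracture healing are documented, and surgeries for fracture healing are a secondary endpoint.
- *The real NPWT and Prontosan risks are left unidentified.* They are in the same protocol, so they count as identified in study documentation. Their absence from the list is an inconsistency without effect on expectedness.
- *The VeraFlo arm is treated differently.* The list applies to both arms, since both receive NPWT.

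The best remaining argument is that the point defeats itself. A UADE must be caused by or associated with the device. If a dressing cannot loosen an implant through load transfer, no UADE is lost; and if it contributes in some other way, the event differs in nature from the listed one. This has force, and it is why the conclusion is worded as a possibility. It does not dispose of the point. The listed wording is broad (weakened bone could be matched to almost any re-fracture in infected bone), and the protocol does not say that a different mechanism makes a different event.

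It can also be said that such events are fairly called anticipated, since the protocol's definition covers events expected from the disease state. That is right, and the fix has to respect it. Being anticipated from the disease is not the same as being identified as an effect of the study device.

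**Conclusion.** The point holds in a limited form. Three of the seven examples describe a device that is not under study, and the list has a function because the UADE and expectedness rules depend on prior identification in the plan. An implant-type event judged device-related could be classed as expected, excluded from UADE status and, if not severe, left outside the 24-hour report.

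This rests on two assumptions: that the investigator judges such an event device-related, and that the list is read as prior identification even where the mechanism differs. The number of events affected cannot be estimated from the protocol, which gives no rate for hardware failure; it is probably small. No endpoint, analysis or sample size depends on the list. Severity is minor to moderate: an error of safety classification that is cheap to correct.

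**What to change.** 1. Delete the three implant items (loosening, dislocation or subluxation, overload fracture) from the device-related list.
2. Reconcile the list with the NPWT risk table and the Prontosan paragraph. A cross-reference is enough.
3. Add a statement that hardware loosening, hardware failure or re-fracture is recorded as an AE or SAE with relatedness judged case by case, and that it is not treated as previously identified as an effect of the NPWT/VeraFlo device, even where it may be anticipated from the underlying disease.

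The cost is protocol wording only; no procedure or analysis changes. The downside is that a few more events may be labelled unanticipated, and some of these would then fall under the 24-hour report.
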